# **B** Secondary Endpoints

Secondary outcome variables will be examined between the two study arms at baseline, pubertal onset and adult height (final visit). To examine sex differences, the secondary outcomes variables will be examined by-sex between the two study arms.

'Pubertal Onset' is defined as the visit when patients entered puberty (Tanner 2 breast in females, testicle size > 3mL) or completed therapy with the aromatase inhibitor and or LHRHa.

- i. Adult height achieved will also be expressed standard deviation (SD) units and in cm as the difference in height achieved in relation to their target height (i.e., mid-parental height, calculated based on their parental heights)
- ii. Height achieved (SD units) from baseline to pubertal onset
- iii. Height achieved (SD units) from pubertal onset to adult height
- iv. Predicted adult height (using Bayley-Pinneau method) at pubertal onset
- v. Predicted adult height (using Bayley-Pinneau method) change from baseline to pubertal onset
- vi. Predicted adult height (using Bayley-Pinneau method) change from pubertal onset to final height
- vii. Growth velocity (in SD units) from baseline to pubertal onset
- viii. Growth velocity (in SD units) from pubertal onset to adult height
- ix. Percent of visits with ACTH in normal range from baseline to pubertal onset
- x. Percent of visits with ACTH in normal range from pubertal onset to adult height
- xi. Percent of visits with androstenedione in normal range from baseline to pubertal onset
- xii. Percent of visits with androstenedione in normal range from pubertal onset to adult height
- xiii. Percent of visits with 17-hydroxyprogesterone in the optimal range (<1,200 ng/dL) or high (>1,200 ng/dL) from baseline to pubertal onset
- xiv. Percent of visits with 17-hydroxyprogesterone in the in the optimal range (<1,200 ng/dL) or high (>1,200 ng/dL) from pubertal onset to adult height
- xv. Percent of patients with onset of central precocious puberty (CPP)

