#### **Protocol**

Before entry into the study, adequacy of the patient's CAH management will be documented. Treatment will be modified as needed to achieve optimal control, according to state-of-the-art concepts of CAH management, as outlined below.

Secondary central precocious puberty will be defined by meeting one or more of the following criteria:

1) Peak Leuprolide-stimulated LH/FSH ratio consistent with central puberty.

3) Baseline LH-ICMA of greater than 0.3 [35].

4) Clinical evidence of central precocious puberty (breast development in girls and testicular enlargement in boys).

Patients who are in secondary central precocious puberty will be offered treatment with a commercially available LHRH agonist, Lupron Depot(administered via monthly intramuscular injection, TAP) or an investigational LHRH agonist, Deslorelin (administered via daily subcutaneous injection). Since 1979, Deslorelin has been used at the NIH for the treatment of

central precocious puberty and has been shown to be safe and effective [35]. Other commercially available products include Histrelin (Roberts) and Lupron Injection, both administered via daily subcutaneous injection. We have chosen to continue to use Deslorelin because it is readily available through the NIH Pharmacy (there was a recent shortage of Histrelin), it is less expensive than the commercially available subcutaneous products, and we have extensive personal experience in its use.

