Choice of medication will be based on patient and family preferences. Families will be counseled on the advantages and disadvantages of these two therapies. Both medications are known to effectively suppress the hypothalamic-pituitary-gonadal axis. Known side effects include rash, and local injection site reactions (milder with Deslorelin). Lupron has the advantage of monthly administration and the disadvantage of an increase risk of local injection site abscess formation (Deslorelin may cause redness at the injection site but has not been reported to result in abscess formation). Lupron also may require more dose adjustments in the beginning of therapy. Anaphylactoid reactions are an extremely rare risk for both medications. Children will return to the NIH day hospital 3 months after starting LHRH analog therapy for evaluation of hypothalamic-pituitary-gonadal suppression. Those patients who are currently being treated with Deslorelin (previously under protocol 79-CH-112) will be continued on Deslorelin or switched to Lupron, depending on patient preference.

Once degree of CAH control has been judged optimal, children will be randomized to receive either the regimen of flutamide, testolactone or letrozole, and reduced hydrocortisone dose or conventional treatment (with hydrocortisone and fludrocortisone) until the age of 13 in the girls and 14 in the boys. At that time the regimen of flutamide, testolactone, and reduced hydrocortisone dose will be discontinued in boys so that the subjects can progress through puberty. At age 13 years, girls who are receiving flutamide and testolactone or letrozole therapy will discontinue the aromatase inhibitor therapy (to allow normal progression of puberty) and continue flutamide (to continue androgen blockade). Flutamide therapy will continue until 2 years after menarche or when final height is reached, whichever occurs first.

Children who are also receiving concurrent LHRH analog to suppress central puberty will also discontinue this agent at age 13 in the girls or age 14 in the boys. The operational definition of age 13 or 14 will be the NIH study visit that is closest to their thirteenth or fourteenth birthday. The operational definition of attainment of final height, as in our other long-term trials, will be the study visit at which the incremental growth over the previous 12 months declines to less than 1.5 cm (0.6 inch).

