If a patient develops premature pubertal activation of the hypothalamic-pituitary-gonadal axis during the study, he or she will receive treatment with an LHRH analog. Since we cannot predict with certainty who may develop secondary central precocious puberty during the study, all patients and their families will receive an explanation of the use of LHRH analogs and available treatment regimens. If a child develops premature pubertal activation of the hypothalamic-pituitary-gonadal axis, the NIH will supply a commercially available LHRH agonist, Lupron (monthly intramuscular injection) or an investigational LHRH agonist, Deslorelin (daily subcutaneous injection) Choice of medication will be based on family preference and demonstrated efficacy in each patient.

Because the degree of control of CAH often varies over time for unexplained reasons, adjustments in total hydrocortisone dose will be permitted during the conventional treatment arm throughout the study, as would be the case in clinical practice. These dose adjustments will be guided by both clinical and biochemical criteria as outlined in the following discussion of the principles that are currently used in managing these patients.

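### The pubertal-onset landmark used in 16 of 19 secondary endpoints can be triggered by completing a drug that only one arm receives, with no stated rule for which trigger governs

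*Combined protocol and SAP*

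**What the plan says.** B Secondary Endpoints compares the arms at baseline, pubertal onset and adult height. Pubertal onset is reached by clinical signs or by finishing treatment: "Tanner 2 breast in females, testicle size > 3mL) or completed therapy with the aromatase inhibitor and or LHRHa". The definition thus has three limbs: clinical signs, completion of the aromatase inhibitor, and completion of the LHRH analog.

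The Protocol subsection of Study Design and Methods randomises children to the flutamide and aromatase-inhibitor regimen "or conventional treatment (with hydrocortisone and fludrocortisone) until the age of 13 in the girls and 14 in the boys". The conventional arm has no aromatase inhibitor to complete. In the investigational arm, boys stop the regimen at 14, and girls at 13 "will discontinue the aromatase inhibitor therapy (to allow normal progression of puberty"). An LHRH analog can be used in either arm, and children on it "will also discontinue this agent at age 13 in the girls or age 14 in the boys". The stopping visit is fixed by birth date: "The operational definition of age 13 or 14 will be the NIH study visit that is closest to their thirteenth or fourteenth birthday".

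The same subsection counts as one criterion for central precocious puberty "Clinical evidence of central precocious puberty (breast development in girls and testicular enlargement in boys"). A child with premature activation "during the study, he or she will receive treatment with an LHRH analog".

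Analysis of Study uses pubertal onset as a repeated-measures timepoint without defining it further, and refers to SAP Appendix A, which was not in the text reviewed.

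**The concern.** A visit at which two randomised arms are compared should be set the same way in both. Here one limb exists in one arm only, and a child can meet two limbs years apart:

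- An investigational-arm child with clinical signs before 13 or 14 meets the clinical limb first and the aromatase-inhibitor limb later.
- A child in either arm who shows signs, starts an LHRH analog and stops it at 13 or 14 meets the clinical limb and the analog limb.
- A conventional-arm child never given an LHRH analog can meet only the clinical limb.

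If drug completion or the latest event governs, investigational-arm windows run to about 13 or 14, while windows for the last group end at clinical signs. The arms are then compared at different ages and over windows of different length. Endpoint xvii counts the years in which bone age stays unchanged between baseline and the landmark, so a longer window alone raises it. SD scores, growth rates and percentages of visits are affected mainly through the ages they cover. Analysis of Study promises adjustment for confounders but names neither landmark age nor window length.

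**Working it through.** **Reach.** There are 19 secondary endpoints. Those naming the landmark are ii–xiv (13) and xvi, xvii and xviii (3): 13 + 3 = 16. Endpoints i, xv and xix do not name it, and xvi and xviii also have components without it. Exploratory ii–iii and the testicular adrenal rest tumor safety endpoint use it. The primary endpoint, adult height in SD units, does not.

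**Size.** The plan gives no figure for landmark age, so there is none to reproduce.

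- From the documents: stopping age c = 13 (girls), 14 (boys).
- Assumed: clinical onset X normal with SD 1 and mean m = 10 (range 9–11.5) in girls and 11.5 (range 10.5–12.5) in boys, equal by arm; the same share p of each arm on an LHRH analog until c; randomisation at age 5; bone age unchanged for 0.1–0.3 years per year in both arms.

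Gaps are investigational minus conventional. Write z = (c − m)/SD, with Φ and φ the standard normal distribution function and density.

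*Earliest event, p = 0.* Gap = E[min(X,c)] − m = (c − m)(1 − Φ(z)) − SD·φ(z). This is 0.00 to −0.03 years over the onset range. With SD 1.5 and the latest means, z = 1: 1.5 × 0.1587 − 1.5 × 0.2420 = −0.12.

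*Latest event, p = 0.* Gap = E[max(X,c)] − m = (c − m)Φ(z) + SD·φ(z). Girls at m = 10: 3.0 years. Boys at m = 11.5: 2.5 years. At the latest means, 1.5 × 0.9332 + 0.1295 = 1.53 in each sex.

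*Latest event, p > 0.* The answer depends on who receives the analog, so two extremes are shown.

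- Use unrelated to onset age: gap = (1 − p)(E[max(X,c)] − m).
- The earliest-onset share p receives it: gap = E[c − X over q < X < c], with q the p-quantile of X. Girls at p = 50%, q = 10: 3 × (0.99865 − 0.5) − (0.3989 − 0.0044) = 1.10.

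| Share on LHRH analog | Girls, unrelated | Girls, earliest-onset | Boys, unrelated | Boys, earliest-onset |
|---|---|---|---|---|
| 0 | 3.0 | 3.0 | 2.5 | 2.5 |
| 25% | 2.25 | 1.93 | 1.88 | 1.56 |
| 50% | 1.50 | 1.10 | 1.25 | 0.85 |
| 75% | 0.75 | 0.43 | 0.63 | 0.31 |

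Over all assumed means and shares, the latest-event gap runs from 0.09 to 4.0 years. If completion always governs, results are nearly the same (at p = 0, c − m = 3.0 and 2.5).

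*Window length from age 5.* At p = 0 the ratio is (13 − 5)/(10 − 5) = 1.60 in girls and (14 − 5)/(11.5 − 5) = 1.38 in boys. At p = 50% it is 1.16–1.23 and 1.10–1.16.

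*Endpoint xvii.* Spurious difference = rate × gap. At p = 0, girls: 0.1 × 3.0 = 0.3 to 0.3 × 3.0 = 0.9 years; boys: 0.1 × 2.5 = 0.25 to 0.3 × 2.5 = 0.75. At p = 50%, girls: 0.1 × 1.10 = 0.11 to 0.3 × 1.50 = 0.45; boys: 0.1 × 0.85 = 0.09 to 0.3 × 1.25 = 0.38. On the earliest-event reading it is about 0.

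**Is earliest event a safe default?** Patient Selection admits children whose puberty has already been activated, provided they are on an LHRH agonist. For those with clinical signs before entry, an earliest-event landmark precedes baseline and leaves no baseline-to-onset window. Some completion rule is needed for them, and the text does not say for whom it applies.

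**The case against.** The strongest reply is that the problem may not exist. A precedence rule for an analysis visit is what a SAP would hold, and Appendix A may hold one. The definition can also be read as whichever comes first, which makes the gap negligible if onset is equal by arm. The completion limb may be meant only for children whose puberty was suppressed. All of this is possible; none of it is stated in the text reviewed, and the earliest-event reading fails for children activated before entry.

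The reply on size largely stands. Analogs are given for premature activation, so users should mainly be early-onset children; the lower end of each range is then the more natural one. The 4.0-year extreme needs girls with mean onset at 9 and nobody on an analog, which sits badly with the protocol's own provisions for early puberty.

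A reader might infer that all 16 endpoints are seriously biased, or that the arms will be assessed years apart. The documents support neither: the gap depends on an unstated rule and on onset ages they do not give, and only xvii is a raw count over the window. A reader might also infer that age-13/14 comparisons should replace the puberty-phase analyses. The Secondary Objectives ask about effects before and during puberty, so those analyses answer a planned question.

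**Conclusion.** The concern holds as a defect in how the landmark is specified. One trigger is available to one arm only, no order of precedence appears in the text reviewed, and the landmark reaches 16 of 19 secondary endpoints. The resulting shift in assessment age is about 0 (to −0.12 years) if the earliest event governs with equal clinical onset. Under the latest event and central assumptions it is 3.0 years (girls) and 2.5 years (boys) without analog use. At shares of 25/50/75% it is 1.9–2.25 / 1.1–1.5 / 0.4–0.75 years in girls and 1.6–1.9 / 0.85–1.25 / 0.3–0.6 in boys. Onset ages, analog share, randomisation age and bone-age rate are assumptions. Confidence is medium because Appendix A was not available. The primary conclusion is not at risk; the change should be made before the secondary endpoints are analysed.

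**What to change.** 1. Express endpoint xvii per year of the baseline-to-landmark window.
2. Keep the puberty-phase analyses for the Secondary Objectives, but state one landmark rule, applied identically in both arms, that does not use aromatase-inhibitor completion as an arm-specific trigger. Include a line for children on an LHRH analog at entry and for those starting it on study. If Appendix A already does this, confirm it.
3. Add, as a supporting between-arm comparison, the same outcomes at the NIH visit nearest age 13 (girls) or 14 (boys), already defined and fixed by birth date, and check that the arm conclusions agree. This matters even under a common rule: analog use follows randomisation and is tied to endpoint xv, "Percent of patients with onset of central precocious puberty (CPP"). If the landmark were the analog stop for users and clinical signs otherwise, a 10–20 point difference in use between arms, among children of average onset, would shift it by 0.1 × 3 = 0.3 to 0.2 × 3 = 0.6 years in girls and 0.1 × 2.5 = 0.25 to 0.2 × 2.5 = 0.5 in boys.
4. Report landmark age and window length by arm.

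The cost is SAP wording and re-derivation from the six-monthly visits already planned. The age-13/14 periods mix pre-pubertal and pubertal growth, and a child already at adult height by then has no second period; report how many by arm. Because the trial is open-label, document that these changes were made without reference to outcome data by arm.

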achieve perfectly physiologic levels, and thus perfectly normal ACTH levels and adrenal size (euplastic adrenals), the adrenals will nonetheless secrete an abnormally high ratio of androgen and estrogen to cortisol because the 21-hydroxylase deficiency shifts an excessive proportion of the steroid intermediates into the androgen and estrogen pathways. This excess androgen and estrogen will, if left unchecked, accelerate growth rate and bone maturation and compromise adult height. If, on the other hand, the hydrocortisone dose is increased above perfectly physiologic levels to control the excess androgen and estrogen production by the 21-hydroxylase-deficient adrenal glands, the resulting iatrogenic hypercortisolism will stunt growth rate, impair adult stature, decrease bone mineral density, alter intermediary metabolism, and cause hypertension. Thus, the existing approach to treatment produces either hypercortisolism, androgen excess, or a combination of these states.

Our hypothesis to improve treatment initially arose from work in the intramural program of NICHD to treat boys with familial male precocious puberty (FMPP). The accelerated growth rate and bone maturation of these boys was controlled effectively with an antiandrogen (spironolactone) and an aromatase inhibitor (testolactone) [8]. We hypothesized that a similar approach would be effective in CAH, and would allow us to avoid the complications of glucocorticoid excess by reducing hydrocortisone dose to strictly physiologic levels. An antiandrogen other than spironolactone will be required in CAH, however, since patients with CAH have a defect of the aldosterone pathway that precludes the use of spironolactone because this drug also has aldosterone antagonist activity. Thus, we have substituted flutamide for spironolactone. The aromatase inhibitor is an essential component of the regimen to prevent the maturational effects of estrogen upon bone, which are exerted at extremely low levels [9–11].

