### Secondary Objectives

- To assess the safety and tolerability of antiandrogen, aromatase inhibitor and reduced hydrocortisone dose combination therapy.
- To assess the effect of antiandrogen, aromatase inhibitor and reduced hydrocortisone dose combination therapy on height gain, growth velocity and bone maturation prior to puberty.
- To assess the effect of antiandrogen, aromatase inhibitor and reduced hydrocortisone dose combination therapy on height gain and bone maturation during puberty
- To assess the effect of antiandrogen, aromatase inhibitor and reduced hydrocortisone dose combination therapy on development of TART in males and establishment of menstrual regularity in females
- To assess the effect of antiandrogen, aromatase inhibitor and reduced hydrocortisone dose combination therapy on fasting glucose, body mass index, and bone mineral density
- To assess hormonal control based on percent of visits within the normal (or optimal) range for 17OHP, androstenedione, PRA and ACTH
- To assess sex differences in outcomes.

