#### Hydrocortisone Dose Adjustment During Investigational Treatment

Congenital adrenal hyperplasia occurs in several clinically distinct variants that reflect differing severity of the underlying enzymatic deficiency, even among the classic forms. For example, the salt-wasting and simple-virilizing forms of 21-hydroxylase deficiency have different clinical courses: salt-wasters experience many more episodes of adrenal crisis and may require more glucocorticoid for adequate control. Even within the salt-waster and simple-virilizer subgroups of CAH, clinical heterogeneity is seen. This may be due to varying genotypes or other unknown factors.

A hydrocortisone dose of 8 mg/m2/day was chosen in our initial pilot study based on estimates of normal production rate; however, children may vary in their glucocorticoid daily requirements. Our hypothesis that the regimen of flutamide, an aromatase inhibitor and a reduced hydrocortisone dose can normalize the growth of children with, CAH while avoiding the complications of supraphysiologic glucocorticoid, does not require identical glucocorticoid doses in all children on the new regimen. Regimens will be more closely tailored to the individual differences in glucocorticoid requirement. The hydrocortisone dose will be allowed to vary in the flutamide-aromatase inhibitor treatment arm.

With plasma renin activity in the normal range, hydrocortisone dose will generally be increased if 2 or more of the following occur:

- 1) the rate of bone age advancement exceeds 2 years per chronologic year and there is no evidence of central precocious puberty as the cause;
- 2) plasma 17-hydroxyprogesterone levels exceed 10,000 ng/dL;
- 3) plasma androstenedione levels exceed 400 ng/dL;
- 4) testosterone levels exceed 100 ng/dL in girls or prepubertal boys;

- 5) signs of virilization (clitoral growth, voice deepening, acne) on physical examination;
- 6) presence of adrenal rest tissue on testicular ultrasound in boys (see below);
- 7) evidence of macronodular disease on adrenal ultrasound or MRI (see below).

With plasma renin activity in the normal range, hydrocortisone dose may be decreased if 2 or more of the following occur:

- 1) plasma 17-hydroxyprogesterone levels are below 500 ng/dL;
- 2) plasma androstenedione levels are below 50 ng/dL;
- 3) the rate of bone age advancement is less than 1 year per chronologic year;
- 4) weight percentile is greater than or equal to height percentile.

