#### Analysis of Study (please also see attached SAP Appendix A)

- The primary outcome (adult height expressed in SD units) will be compared between groups at the conclusion of the study using the unpaired two-tailed Student's t-test, or nonparametric Wilcoxon rank sum test, as appropriate
- Secondary outcome measures during the study include hormone levels (percent of visits in ranged defined above) and treatment doses, BMI (as SD units), final BMD (Z-score), growth velocity (in SD units), rate of bone maturation, and predicted adult height (Bayley-Pinneau method, automated software in a subset of patients) at baseline, pubertal onset, and final visit. These outcomes will be compared between the study arms by multivariable mixed models for repeated measures. These models will allow for within-subject comparisons between timepoints, as well as account for their correlations across time, adjust for potential confounders, and specify the appropriate outcome distribution (e.g., normal, binomial, or Poisson distribution for type of data). They are a robust method for accommodating missing data, especially in measures that are repeated and collected longitudinally. Post-hoc comparisons will identify the driving factors and group effect influencing any observed differences, and will be corrected for multiple comparisons as applicable.

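### Scoring ACTH and androstenedione only as in or out of normal range loses the direction of any arm difference; for 17-OHP the single cut has no floor and no grading above it

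*Combined protocol and SAP*

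**What the plan says.** The Secondary Objectives define the aim as: "To assess hormonal control based on percent of visits within the normal (or optimal) range for 17OHP, androstenedione, PRA and ACTH". Secondary Endpoints ix to xii apply this to ACTH and androstenedione, before and after pubertal onset: "Percent of visits with ACTH in normal range from baseline to pubertal onset" and "Percent of visits with androstenedione in normal range from baseline to pubertal onset". No limits are given for either normal range. Endpoints xiii and xiv treat 17-OHP differently: "Percent of visits with 17-hydroxyprogesterone in the optimal range (<1,200 ng/dL) or high (>1,200 ng/dL) from baseline to pubertal onset".

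Analysis of Study repeats the measure: "Secondary outcome measures during the study include hormone levels (percent of visits in ranged defined above) and treatment doses". The supplied text names no analysis of the hormone level itself and no split of out-of-range visits into low and high. The same section plans multivariable mixed models for repeated measures for these outcomes.

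Other sections give direction a meaning. The Introduction says of glucocorticoid dosing: "Thus, the existing approach to treatment produces either hypercortisolism, androgen excess, or a combination of these states". On the investigational regimen, androstenedione below 50 ng/dL is a criterion for lowering hydrocortisone and above 400 ng/dL a criterion for raising it. The 17-OHP criterion for raising it there is "plasma 17-hydroxyprogesterone levels exceed 10,000 ng/dL", and two or more criteria are needed. On conventional treatment, 17-OHP of 500 to 1,300 ng/dL is called appropriate, an increase is considered from 1,300 with further steps at 3,000 and 6,000, and a decrease is considered below 500 and more strongly below 200.

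**The concern.** A normal range for ACTH or androstenedione has two sides. An in-range share merges a visit that is too low with one that is too high, yet the protocol reads the first as a sign of too much glucocorticoid and the second as a sign of too little control. One arm is titrated to hold hormones down; the other is allowed to run high while the androgen receptor and aromatase are blocked. Departures in opposite directions are therefore a foreseeable result of this design. If they occur, the two arms can score the same while their levels differ, and a difference in score does not say which arm is suppressed.

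For 17-OHP, low and high values are scored apart. The faults are that a visit below 500 ng/dL counts as optimal, which does not agree with the dose-adjustment section, and that 1,300 and 9,000 ng/dL receive the same score.

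At stake is the interpretation of the hormonal-control objective. The adult-height comparison is untouched.

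**Working it through.** **The plan's own figure.** The only power statement concerns adult height: SD 6 cm, two-sided 0.05, 80% power, 24 per group for 5 cm and 17 for 6 cm. With the exact t-test the noncentrality is (5/6)·√(24/2) = 2.89, power 81%, and (6/6)·√(17/2) = 2.92, power 81%. These are the smallest sizes reaching 80%, so both figures reproduce. I use 24 per arm below only as a realistic number of completers.

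**Assumptions for the hormones (none is in the documents).** Log-normal levels; natural-log SD 0.7 between and 1.0 within child; 10 visits per child; a two-fold difference between arms. The androstenedione range is varied. The 50-400 ng/dL case borrows the dose-adjustment criteria, which are not a normal range.

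**Shares in one visit.** Total log-SD = √(0.7² + 1.0²) = 1.22. Share below limit L at median m = Φ(ln(L/m)/1.22); share above U = 1 − Φ(ln(U/m)/1.22). With range 50-400:

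- Median 100: below Φ(−0.57) = 29%, above 1 − Φ(1.14) = 13%, in range 59%.
- Median 200: below 13%, above 29%, in range 59%.

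The scores are identical and the low/high split is reversed. This follows from the choice of medians: 100 × 200 = 50 × 400, so the arms are log-symmetric about the range.

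**Power of mean log level.** SD of a child's mean = √(0.49 + 1.00/10) = 0.768. Standardised difference = ln 2/0.768 = 0.90. Noncentrality = 0.90·√(24/2) = 3.13, which gives 86%.

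**Power of percent-in-range.** Simulated, with at least 4,000 trials per scenario and a t-test on each child's percent of visits in range. The planned mixed model could differ somewhat, but if fed the same in-range indicator it has no more information on direction.

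| Androstenedione range (ng/dL) | Medians | Percent-in-range | Mean log level |
|---|---|---|---|
| 50-400 | 100 v 200 | 5% | 86% |
| 50-200 | 100 v 200 | 18% | 86% |
| 50-400 | 200 v 400 | 53% | 86% |
| 20-200 | 100 v 200 | 61% | 86% |
| no lower limit, upper 400 or 200 | 100 v 200 | 75-80% | 86% |

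Exact symmetry is not required for a large loss: with range 50-400 and medians 70 v 200, power is about 14% against over 99%.

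**17-OHP, missing floor.** Take a median of 150 ng/dL and a visit log-SD of 1.0. Share scored optimal = Φ(ln(1200/150)) = Φ(2.08) = 98%. Yet Φ(ln(500/150)) = Φ(1.20) = 89% of visits are below 500 ng/dL, and 61% are below 200. Over log-SDs of 0.8 to 1.3 the optimal share is 99.5% to 94.5%. An arm with median 3,000 scores 18% at log-SD 1.0, so opposite movements in 17-OHP do separate.

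**17-OHP, lost grading.** Same SDs as for androstenedione, two-fold difference, 6 to 12 visits. Analysing level instead of the 1,200 ng/dL cut gains about 4-8 points of power at medians 1,000 v 2,000 and about 20-27 points at 4,000 v 8,000 (for 6 visits, roughly 55% against 82%).

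**The case against.** **The 5% figure is built in.** This is correct. It needs medians symmetric about an assumed range. If the lower limit of normal for androstenedione is close to zero, few visits can fall below it and most of the loss disappears. If both arms sit high and differ three-fold (200 v 600 with range 50-400), percent-in-range has about 95% power. A reader might infer that the endpoint is blind to arm differences in general. The documents do not support that, because they state neither the limits nor any distribution.

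**Opposite shifts are possible, not shown.** Samples are taken near 0800 with the morning hydrocortisone held, and the conventional-treatment rules consider dose decreases to avoid over-suppression. This lowers the chance of many suppressed visits but does not remove it.

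**Low and high 17-OHP might be thought to count alike too.** They do not: the cut is one-sided.

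**Percent-in-range is the measure that the objective names.** A geometric mean answers a different question and has its own blind spot: a child who alternates between suppressed and high values can average to normal. Raw levels also change with age, sex and puberty, which a suitable reference range could absorb. This stands, and it argues for adding a level analysis rather than substituting one.

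**Other endpoints carry some of the information.** Hydrocortisone dose, cumulative glucocorticoid exposure, growth velocity and bone maturation point indirectly to direction, but none reports the hormonal response itself.

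**The SAP is cited as Appendix A and is not in the supplied text.** It may already contain an analysis of levels.

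**Conclusion.** The point holds in limited form. For ACTH and androstenedione, the listed endpoints cannot tell suppression from excess, in a trial whose rationale turns on that distinction and whose arms are run to different levels. The loss of direction follows from the definition and needs no distributional assumption. The loss of power does: for a two-fold androstenedione difference it ranges from almost complete (about 5% against 86%) to modest (75-80% against 86%), depending on normal limits that the plan does not state.

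For 17-OHP, the absence of a floor does not agree with the 500-1,300 ng/dL range in the conventional-treatment section, and the two sections must be reconciled. The loss from not grading high values is small near the cut and larger where levels are high.

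This concerns a secondary objective. It does not bear on the adult-height conclusion, and it does not show that percent-in-range is the wrong endpoint. It is worth correcting because the correction is cheap.

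**What to change.** 1. Keep percent of visits in range as the stated endpoint, and state the reference limits used for ACTH and androstenedione.
2. For endpoints ix to xii, report and compare by arm the percent of visits below, within and above the age- and sex-appropriate range.
3. For endpoints xiii and xiv, tabulate visits by the 17-OHP bands in the conventional-treatment dose-adjustment section, including below 500 ng/dL, and reconcile the 1,200 ng/dL cut with those bands.
4. In Analysis of Study, add a supportive repeated-measures mixed model of log hormone level over all visits in each window, adjusted for age, sex and pubertal stage, reported as the geometric mean ratio between arms with a 95% confidence interval.

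If Appendix A already contains items 2 to 4, a cross-reference from the endpoint list is enough.

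The cost is endpoint and SAP wording and a few more runs on data already collected, within the model framework already planned. The drawbacks are a few extra secondary estimates and the need for a rule on values below the assay limit.
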